### **14.3.2 Other efficacy analyses**

For the CIDP relapse (Yes/No) up to Week 13 (Day 85) after first treatment according to iRODS, adjusted INCAT, and maximum grip strength assessed by the site personnel scores, treatment comparison versus placebo for the rozanolixizumab group (differences in CIDP relapse rates) will be performed using a standard 1-sided Wald asymptotic test with a 5% alpha level. The corresponding 2-sided 90% CI for the difference will be constructed using the asymptotic standard error (asymptotic Wald confidence limits). Sensitivity analyses for relapse will be performed and described in the SAP.

For the analysis, subjects who withdraw for any reason before Week 13 (Day 85) or who have missing data at Week 13 (Day 85) will be considered as relapsed. The same is true for subjects administered an Ig infusion rescue medication during this time interval.

Kaplan-Meier estimates and log-rank tests will be used to compare the treatment difference for the time to CIDP relapse (according to iRODS, adjusted INCAT scores, and maximum grip strength assessed by site personnel).

The statistical methods applied for the variables derived from rescue medication (subject received rescue medication [Yes/No] and time to rescue medication administration) will be the same as those for the CIDP relapse and time to CIDP relapse.

For the change from Baseline at each scheduled assessment during the Treatment and Observation Period, iRODS score, adjusted INCAT score, maximum grip strength assessed by the site personnel score, and RT-MRC sum score, treatment differences will be compared by

ANCOVAs adjusted for Baseline measurement and prior Ig therapy. Analyses will be performed for the FAS utilizing the observed cases.

The results of the newly developed PROs (CIDP PRO instrument and fatigue scale) will be listed and frequency tables will be provided at an item level. A psychometric analysis plan will be created, which will detail all the exploratory and correlation analyses between the newly developed PROs and clinical variables. The PROs will also be subject to a Rasch analysis. The results of the psychometric analyses will be reported separately from the clinical study report (CSR).

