## 2.4 Determination of sample size

Due to the pilot character of the study, the sample size is chosen based on both the statistical considerations and practical limitations (eg, to recruit sufficient subjects in a reasonable time to achieve the objectives of the study) and to establish whether a positive trend towards active treatment can be established. For this reason, a one-sided exploratory test is considered appropriate in this setting.

Since no data is currently publicly available on the primary outcome measure in this indication, the sample size is based on assumptions about the likely effect size. Thus, the sample size considerations are only based on assumptions for the effect size index (difference in group means/SD). When the sample size in each group is 15, a 1-sided 5.0% t-test for the comparison of rozanolixizumab and placebo will provide 80% power to detect a statistically significant difference in case there is a large effect of rozanolixizumab with an effect size index of 0.93. In case of a medium index (0.52) the power already decreases to 40%. It will be assumed that 10% of the randomized subjects cannot be utilized for the efficacy analysis; hence 34 subjects will be randomized.

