### **4.2 Handling of dropouts or missing data**

#### **4.2.1 Efficacy data**

For participants who prematurely withdraw for any reason before Week 13 (Day 85), data collected during the PEOT Visit will be used to impute iRODS, INCAT and grip strength at the closest missing visit. In case a participant discontinues the study prematurely, the assessment of the PEOT visit will be mapped to closest missing visit according to the visit schedule utilizing the relative day in study to a maximum of day 85 (Visit 17). However, if a participant receives rescue medication prior to the PEOT visit, the assessment will be regarded invalid and only listed. Assessments on the same day as first intake of rescue medication is acceptable for analysis.

Since the analysis is based on the mixed model repeated measures (MMRM) approach, visits beyond the PEOT Visit will not be imputed. Missing data in-between visits will be covered by the MMRM approach.

For additional analyses of iRODS score to account for missing data, last observation carried forward (LOCF) and multiple imputation will be applied to address the issue of missing scores (see Section 8.1.3). There will be no imputation of missing individual item scores in the summaries for the iRODS; only to the overall iRODS score.

For the analysis of relapse data, participants who withdraw from the study for any reason before Week 13 (Day 85) or who have missing data at Week 13 (Day 85) will be considered as relapsed and analysed as such. The same is true for participants administered an Ig infusion rescue medication during this time interval.

Participants are asked to record three grip strength score assessments at each day. The efficacy parameter will be derived from grip strength scores taken by a participant up to five days prior to the first IMP (for Baseline value) or visit date (for post Baseline visit value):

1. Maximum of grip strength assessments available at a particular day
2. Mean of maximum grip strength over most recent three non-missing days - up to a maximum of five days

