## 8 EFFICACY ANALYSES

All analyses of the efficacy variables will be performed on the FAS. Additional outputs may be repeated for the PPS or the MFAS where indicated. Listings will be based on the SS.

Treatment group assignment for efficacy analysis will be according to the actual treatment regimen.

All efficacy analyses are to be interpreted as exploratory analyses. No p-values will be presented.

Any efficacy measurements are considered invalid, if the participant received rescue medication before the assessment. Assessments collected at the same day as first intake of rescue medication are considered valid. Respective measurements will not be used for summary tables and MMRM, but kept in listings. This includes iRODS, INCAT, clinician reported grip strength, RT-MRC, CIDP PRO and Fatigue, PGIS, PGIC and the patient reported grip strength as derived in Section 8.2.4.

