## 8.2 Statistical analysis of the other efficacy variables

### 8.2.1 CIDP relapse, MMRM and summary tables will be performed on the FAS and repeated for the PPS for iRODS, adjusted INCAT and clinician reported grip strength.CIDP relapse (iRODS)

CIDP relapse (iRODS) is defined as a clinically important deterioration from Baseline in iRODS score, i.e. a standardized change from baseline smaller than or equal to the minimum clinically important differences-standard error (MCID-SE) of  $\leq -1.96$ .

This standardized change from baseline refers to individual person-level responsiveness calculated by individual change divided by their corresponding SE of difference at a given timepoint. [Va15]

$$\text{"MCID - SE"} = \frac{\text{Standardized value}_{\text{Visit}} - \text{Standardized value}_{\text{Baseline}}}{\sqrt{\text{SE}_{\text{Visit}}^2 + \text{SE}_{\text{Baseline}}^2}}$$

Values and changes from Baseline in iRODS scores will be summarized by treatment group and for all participants and listed by treatment group at each scheduled assessment during the Treatment and Observation Period.

The point estimate and the corresponding 2-sided 90% CI for the difference between placebo and rozimab CIDP relapse rates up to week 13 will be reported. The CI will be constructed using the asymptotic standard error (asymptotic Wald confidence limits).

Analyses will be performed for the FAS utilizing the observed cases.

Sensitivity analysis for relapse will be performed in the same way, however for the PPS.

The rule for handling missing data is described in Section 4.2.1.

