#### **8.2.5 CIDP relapse**

The event of CIDP relapse is defined by occurrence of either relapse across the 3 calculated criteria: iRODS relapse, adjusted INCAT relapse and maximum grip strength as assessed by site personnel (14 kPa) relapse as defined in sections 8.2.1, 8.2.2 and 8.2.3 and 'other' as captured in the CRF by the investigator. It will be described and analysed in the same way as the individual relapse definitions. This will be done for the FAS and the PPS.

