### 8.2.9 Use of rescue medication

The percentage of participants with concomitant medication identified as rescue medication [Yes/No] in the eCRF and time to first rescue medication administration will be summarized by treatment group and for all participants and listed by treatment group at each scheduled assessment during the Treatment and Observation Period.

If a participant receives rescue medication at multiple times, the relative day of the first occurrence is used to define the time to rescue medication.

The statistical methods applied to use of rescue medication and time to use of rescue medication will be the same as for CIDP relapse (iRODS), see Sections 8.2.1 and 8.2.1.1. The rule for handling missing data is described in Section 4.2.7.

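### The 90% Wald intervals for differences in relapse and rescue proportions cover only about 87% on average at 15 to 17 participants per arm; score limits would restore the stated level

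*SAP*

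**What the plan says.** SAP 8.2.1 asks for the point estimate and "corresponding 2-sided 90% CI for the difference between placebo and rozimab CIDP relapse rates up to week 13", and fixes the method: "The CI will be constructed using the asymptotic standard error (asymptotic Wald confidence limits". Protocol 14.3.2 has the same interval, "constructed using the asymptotic standard error (asymptotic Wald confidence limits", there paired with a 1-sided 5% Wald test.

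The method then spreads by cross-reference:
- SAP 8.2.2 applies it to adjusted INCAT relapse, and SAP 8.2.3 to grip-strength relapse at both the 14 kPa and 8 kPa cut-offs.
- SAP 8.2.5 says of the combined relapse event: "It will be described and analysed in the same way as the individual relapse definitions".
- SAP 8.2.9 says the methods for rescue use "will be the same as for CIDP relapse (iRODS), see Sections 8.2.1 and 8.2.1.1".
- The relapse analyses are repeated on the PPS.

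On size, SAP 2.4 reads "When the sample size in each group is 15" and plans 34 randomized. On missing relapse data, SAP 4.2.1 says that participants who withdraw early or "who have missing data at Week 13 (Day 85) will be considered as relapsed and analysed as such"; Ig rescue is treated the same way. On status, SAP 8 states: "All efficacy analyses are to be interpreted as exploratory analyses. No p-values will be presented". Neither document plans an exact, score or continuity-corrected interval, and neither gives an expected relapse or rescue rate.

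**The concern.** The Wald interval for a difference in proportions plugs the observed rates into the variance and centres a normal interval on the observed difference. With 15 to 17 per arm the outcome is a count out of 15 to 17, and both steps are rough. An arm with no events, or with all events, contributes zero variance. The limits can therefore have a true level below the one printed beside them.

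This matters because little else is left. SAP Amendment 2 removed the inference tests and p-values, and the time-to-relapse output in SAP 8.2.1.1 consists of Kaplan-Meier curves with medians by arm. These intervals are the only between-arm inference on the relapse and rescue proportions. If they are labelled 90% but cover less, readers will see more precision than the data support. That works against the stated reason for dropping p-values, which was to avoid overinterpretation.

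**Working it through.** **Inputs.** Confidence level 90%, two-sided, z = 1.645 (SAP 8.2.1). n = 15 per arm (SAP 2.4), and n = 34/2 = 17 per arm from 1:1 randomization (SAP 2.3, 2.4). True rates are an assumption: every pair from 5% to 95% in steps of 5%, which gives 19 × 19 = 361 pairs.

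**The plan's own figures first.** A noncentral t with 28 degrees of freedom, 1-sided 5%, gives power 0.799 at effect size 0.93 and 0.399 at 0.52, matching the stated 80% and 40%. 30/(1 − 0.10) = 33.3, rounded up to an even number, gives 34. The size of 15 to 17 per arm is sound as an input.

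**Method.** With d = p̂₁ − p̂₂ (active minus placebo), the Wald limits are

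d ± 1.645 × √[p̂₁(1 − p̂₁)/n + p̂₂(1 − p̂₂)/n].

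For each pair of true rates, coverage is the sum of the binomial probabilities of all (n + 1)² outcome pairs whose interval contains p₁ − p₂. No simulation is involved. Newcombe hybrid-score and Miettinen-Nurminen (MN) limits were run the same way.

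**Results (n=15 / n=17 per arm).**

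| Quantity | Wald | Newcombe | MN |
|---|---|---|---|
| Mean coverage, rates 5–95% | 87.0% / 87.4% | 90.2% / 90.7% | 90.0% / 90.3% |
| Rate pairs with coverage below 88% | 65% / 61% | 9% / 4% | 9% / 1% |
| Mean coverage, rates 20–80% only | 87.4% / 87.7% | 89.3% / 89.9% | 90.1% / 90.0% |
| Mean benefit-overstating tail, active below placebo (nominal 5%) | 7.5% / 7.3% | 3.7% / 3.5% | 4.9% / 4.7% |

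Within 20–80% the lowest Wald coverage is 85.0% / 85.2%, so the shortfall does not come from extreme rates alone.

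**Single pairs at n=17.**
- 10% vs 60%: Wald 85.5%, with an overstating tail of 9.9%; MN 88.7%.
- 5% vs 20%: Wald 86.3%, and here the excess error (8.8%) understates benefit; MN 90.7%.
- 30% vs 60%: Wald 89.4%, MN 89.7%.

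**Equal true rates.** Averaged over the diagonal of the grid, Wald covers 90.1% / 89.1%. The chance at n=17 that the upper limit falls below zero (nominal 5%) is 6.2% for Wald and 4.9% for both score methods at a rate of 20%, 6.0% and 4.9% at 30%, and 6.1% for all three at 50%.

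**Does the reading of zero change?** Take 2/17 vs 6/17. Then d = 0.1176 − 0.3529 = −0.2353, the standard error is √(0.00611 + 0.01343) = 0.1398, and the half-width is 1.645 × 0.1398 = 0.2299. Wald gives [−0.465, −0.005], Newcombe [−0.448, +0.006] and MN [−0.462, +0.008]. At n=17 the reading differs only for 2 vs 6 and 11 vs 15 events, which is 4 of 18² = 324 outcome pairs counting both directions. The chance of such an outcome in favour of active is 5.0% at 10% vs 30%, 3.5% at 20% vs 40% and 0.1% at 30% vs 60%.

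**Width.** Wald limits are not simply too narrow. Newcombe is narrower than Wald in 60% / 59% of outcome pairs and MN in 55% / 57%. Where the limits sit matters as well as how long they are.

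**Zero-width intervals.** These need both arms at 0% or 100%. For relapse this should be rare, because withdrawal, missing Week 13 data and Ig rescue all count as events. That protection does not extend to rescue use, which SAP 8.2.9 sends to the partial-date rules of SAP 4.2.7. With a true rate of 5% in both arms and n=15, the probability is (0.95¹⁵ + 0.05¹⁵)² = 0.21; at 10% it is 0.04.

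**The case against.** The strongest reply is that very little turns on this. The analyses are exploratory, no decision rule reads the limits, and by the figures above the reading of zero changes in 4 of 324 outcome pairs, with limits that move by about 0.01. That stands, and it sets the priority.

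Second, the 87% is an unweighted average over rates the documents do not give, so 5% vs 95% counts as much as 30% vs 50%, and the 88% cut-off is equally a choice. With equal rates coverage is essentially nominal, and several moderate contrasts at n=17 are only 1 to 2 points short (30% vs 50%: 88.5%). This is fair. However, limiting the range to 20–80% hardly moves the average, and at n=15 the 30% vs 50% pair drops to 86.3%.

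Third, FAS denominators may be nearer 17 than 15, because missing data count as relapse and the FAS needs only one valid post-Baseline iRODS. That is plausible, but the n=17 shortfall is 2.6 points against 3.0, and the PPS may be smaller.

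Fourth, the method is pre-specified consistently in both documents, and score limits do not win everywhere: at 10% vs 30% with n=15, Wald covers 88.9% and MN 86.9%. Both points are true. Consistency does not give an interval its stated level, and across the range MN is much closer to it.

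Finally, the enumeration assumes one common risk within each arm. If risk differs by prior Ig route, the stratification factor, the unstratified interval would be somewhat conservative. That effect was not quantified and is probably small.

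**Conclusion.** The concern holds. At the planned size, the intervals labelled 90% for relapse and rescue differences cover about 87% on average, some 3 points short, and on average the excess error overstates benefit when active is better. At particular rate pairs it can fall in the other tail. The size rests on an assumed uniform spread of true rates from 5% to 95%, independent binomial counts, and 15 to 17 per arm. The shortfall is close to nil on average when the true rates are equal. The primary result is not touched and few observed outcomes would be read differently, so this is an inexpensive improvement of low to moderate priority.

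**What to change.** In SAP 8.2.1, replace the sentence naming Wald limits with: 'The CI will be constructed using Miettinen-Nurminen score limits.' Newcombe hybrid-score limits are an acceptable alternative; MN has the better balanced tails here. Add one line to SAP 3.9, which already lists departures from the protocol-defined analyses. SAP 8.2.2, 8.2.3, 8.2.5 and 8.2.9 inherit the change by cross-reference, and no protocol amendment is requested.

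The cost is one procedure option and two lines of text. Individual intervals may come out wider or narrower than Wald, with no systematic loss of precision.

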#### 8.2.1.1 Analysis of time to CIDP Relapse (iRODS)

The time to CIDP relapse (iRODS) is defined as the time from starting treatment (Day 1) to achievement of iRODS and will be displayed using a Kaplan-Meier curve.

Summary tables will include descriptive statistics. The point estimate for the median number of days to CIDP relapse with 90% CIs will be given if estimable. A summary including the number and percentage of censored participants, the number of relapsed participants and total participants by treatments and in total will be given. Participants withdrawing from the study will be handled as relapsed (see Section 4.2.1).

For the purpose of the analysis participants with no relapse will be censored at the end of the study.

Analyses will be performed for the FAS and repeated for the PPS.

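### With the log-rank tests removed, the SAP plans no between-arm estimate of delay for time to relapse or time to rescue

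*SAP*

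**What the plan says.** Protocol 14.3.2 plans a formal comparison: "Kaplan-Meier estimates and log-rank tests will be used to compare the treatment difference for the time to CIDP relapse", for each of the three scored relapse definitions, with the same methods for time to rescue.

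The SAP withdraws it. Section 8 treats all efficacy analyses as exploratory and presents no p-values. Section 14.2.2.5 (Amendment 2, Change 5) records that inference tests were taken out so that statistical significance would not be over-read. Section 3.9, which lists departures from protocol-defined analyses, does not mention the log-rank tests.

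For time to relapse, SAP 8.2.1.1 keeps a Kaplan-Meier curve, descriptive statistics, counts of relapsed and censored participants by arm, and a median: "The point estimate for the median number of days to CIDP relapse with 90% CIs will be given if estimable". No hazard ratio, difference in medians or restricted mean is named.

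The same methods apply to adjusted INCAT (8.2.2), site-assessed grip strength at the 14 and 8 kPa thresholds (8.2.3) and the composite (8.2.5). For rescue, 8.2.9 says that the methods for rescue use and "time to use of rescue medication will be the same as for CIDP relapse (iRODS", pointing to 8.2.1 and 8.2.1.1.

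For the binary version of the same events, SAP 8.2.1 keeps the difference in rates up to Week 13 with a 2-sided 90% Wald interval.

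**The concern.** Dropping p-values does not require dropping estimates. The SAP itself makes that distinction: it keeps arm differences with 90% CIs for the MMRM variables (8.1.2, 8.2.2 to 8.2.4, 8.2.6) and for relapse rates (8.2.1). The time-to-event variables lost their only planned comparison and received nothing instead.

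Five relapse definitions plus rescue are affected, and both documents list time to event as an efficacy variable for iRODS, INCAT, grip strength and rescue. A reader of the report would see curves and counts but no figure, with its uncertainty, for how long relapse or rescue was put off. In a pilot that reports estimates only, a missing estimate means a missing result.

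Per-arm medians are a weak substitute. The more effective the drug, the less likely its arm is to reach a median.

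**Working it through.** **Sample size inputs (SAP 2.4).** "When the sample size in each group is 15, a 1-sided 5.0% t-test" gives "80% power to detect a statistically significant difference" at an "effect size index of 0.93". "In case of a medium index (0.52) the power already decreases to 40"%. It is assumed that "10% of the randomized subjects cannot be utilized for the efficacy analysis; hence 34 subjects will be randomized".

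**The plan's own figures reproduce.** Noncentral t, df = 28, one-sided 5%, noncentrality d × √(15/2):
- d = 0.93: 0.93 × 2.739 = 2.547, power 79.9%.
- d = 0.52: 0.52 × 2.739 = 1.424, power 39.9%.
- 30 / 0.9 = 33.3, rounded up to 34.

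So each arm has about 15 evaluable or 17 randomized participants. No event rate, event count or power is stated for any time-to-event variable, so the event rates below are assumptions.

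**When a median exists.** The Kaplan-Meier median is the first time S(t) falls to 0.5 or below. With no censoring before Day 85, S = (n − events)/n:
- n = 15: 7 events leave 8/15 = 0.533 (not reached); 8 leave 7/15 = 0.467 (reached).
- n = 17: 8 events leave 9/17 = 0.529 (not reached); 9 leave 8/17 = 0.471 (reached).

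P(reached) = P(X ≥ 8), X ~ Bin(15, p), or P(X ≥ 9), X ~ Bin(17, p):

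| True rate to Day 85 | n = 15 | n = 17 |
|---|---|---|
| 20% | 0.4% | 0.3% |
| 30% | 5% | 4% |
| 40% | 21% | 20% |
| 50% | 50% | 50% |
| 60% | 79% | 80% |
| 70% | 95% | 96% |
| 80% | 99.6% | 99.7% |

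A finite upper 90% limit for the median (log-log limits, Greenwood variance) needs 11 of 15 or 12 of 17 events. At a 60% rate that happens 22% or 26% of the time.

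**Both medians together, and what the alternatives would give (17 per arm).** P(both) is the product of the two arm probabilities.

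For the hazard ratio, assuming proportional hazards, HR = ln(1 − p_roz)/ln(1 − p_plc), with SE(log HR) = 2/√events. At 60% versus 30%, HR = 0.357/0.916 = 0.39, events = 17 × 0.9 = 15.3, SE = 0.511, and the 90% CI is 0.39 × exp(±1.645 × 0.511).

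The restricted mean difference comes from a simulation with exponential times, detection at the next weekly visit and an 84-day horizon. Half-width is 1.645 × √(s₁²/17 + s₂²/17).

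| Placebo vs rozanolixizumab | P(both medians) | HR (90% CI) | Restricted mean difference, days (average 90% half-width) |
|---|---|---|---|
| 30% vs 15% | under 0.1% | 0.46 (0.14 to 1.50) | 6 ± 11 |
| 60% vs 30% | 3% | 0.39 (0.17 to 0.90) | 15 ± 15 |
| 70% vs 40% | 19% | 0.42 (0.20 to 0.91) | 16 ± 15 |
| 80% vs 50% | 50% | 0.43 (0.21 to 0.87) | 18 ± 16 |

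Coverage of the nominal 90% restricted-mean interval in the simulation was 88% to 89%.

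**The time window.** SAP 2.2.1.2 confines these variables to the Treatment Period, but 8.2.1.1 censors non-relapsers at the end of the study. Follow-up after the last dose runs from 1 week (immediate OLE entry) to 24 weeks (SAP 2.3, 3.2.2). A curve run to the end of the study would therefore have a tail from participants who did not enter the OLE directly. As an illustration, take 15 participants: 3 relapse early, 10 leave at Visit 17, and 1 of the remaining 2 relapses later. S = 12/15 × 1/2 = 0.4, so a median is reached on 4 events and rests on off-treatment time.

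**The case against.** The strongest reply is that the removal was deliberate, recorded and reasoned in SAP 14.2.2.5, in a small exploratory pilot where any time-to-event estimate will be imprecise. Log-rank power at 17 per arm would be about 29% at 30% versus 15% and 63% at 80% versus 50%. This stands as a reason against testing. It does not stand against an estimate, since the SAP gives 90% CIs for other variables at the same sample size.

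A reader might infer three stronger things that the documents do not support.

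- **That the median is all that remains.** The curve, the counts and the Week 13 rate difference with its 90% CI also remain, for every relapse definition and for rescue. Timing can be seen in the curve; it is just not estimated between arms. Nor are these the only efficacy variables without an arm difference: the CIDP PRO, fatigue, PGIS and PGIC have none.
- **That an arm's median will usually not be estimable.** No event rate is given. The claim is true below 50% and false above it. A placebo rate above 50% is plausible: participants are Ig-dependent, Ig is prohibited during treatment, and withdrawal, missing Week 13 data and Ig rescue all count as relapse (SAP 4.2.1).
- **That the change was hidden.** Its absence from section 3.9 is a cross-reference gap.

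The proposed estimates also have limits. A restricted mean exists for an arm with no events, but its estimated variance is then zero and the usual interval is too narrow. A hazard ratio needs events in both arms.

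**Conclusion.** The gap is real but moderate. After the log-rank tests were removed, no between-arm time-to-event estimate is planned for any relapse definition or for rescue. Whether events occur is compared; delay is not. Under a useful effect, a comparison of medians would often be unavailable: both are reached about 3% of the time at 60% versus 30%, 19% at 70% versus 40%, and 50% at 80% versus 50%.

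These figures rest on assumed event rates, 17 per arm and no censoring before Day 85; 15 per arm gives nearly the same result. The absence of an estimate rests on the SAP text alone. The primary analysis is unaffected.

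**What to change.** In SAP 8.2.1.1, carried by cross-reference to 8.2.2, 8.2.3, 8.2.5 and 8.2.9:

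1. Add the difference, rozanolixizumab minus placebo, in restricted mean relapse-free time (rescue-free time in 8.2.9) from Day 1 to Day 85, with a 2-sided 90% CI and no p-value. A hazard ratio with 90% CI is an acceptable alternative when both arms have events.
2. For this analysis, censor participants without an event at Day 85 instead of at the end of the study. This fits a Treatment Period variable and matches the horizon of the Week 13 rate difference.
3. If an arm has no events, report the estimate and say that the standard interval is not relied on.
4. List the dropped log-rank tests in SAP 3.9.

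The cost is SAP wording and one extra row per table, with no new data. The downside is wide, slightly approximate intervals at 15 to 17 per arm. Timing will also be coarser for INCAT and site grip strength, which are assessed about every two weeks from Visit 8, than for iRODS, which is weekly.
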